Compression Wraps as adjuvant therapy in the management of acute systolic heart failure (CATAS-HF trial)

8/1/2020

- Study Protocol &
Statistical Analysis Plan

NCT# NCT04095416

STUDY TITLE: Compression wraps as adjuvant therapy in the management of acute systolic heart failure (CATAS-HF)**• STUDY AIM, BACKGROUND, AND DESIGN ABSTRACT**

Our goal is to measure the application of lower extremity compression wrapping as adjuvant therapy to diuresis in the management of patients hospitalized for acute systolic heart failure. Use of compression wrapping will be assessed through randomized parallel intervention clinical trial of patients admitted to Henry Ford Hospital I5 Cardiology service for management of acute systolic heart failure presenting with lower extremity edema. Enrolled patients will be managed with standard medical therapy, with (intervention) or without (control) the adjuvant use of lower extremity compression wrapping. Efficacy of the intervention will be analyzed for the following primary endpoints: 1) Percentage difference in weight before and after diuresis 2) Percent difference in Brain natriuretic peptide (BNP) from admission to discharge; 3) Difference in length of admission in days. Our hypothesis is adjuvant use of lower extremity compression wraps to standard medical therapy increases percentage of weight reduction achieved with diuresis, increases percent reduction in BNP after diuresis, and decreases total length of stay for patients hospitalized with acute systolic heart failure.

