Lower extremity compression wraps are a low cost inpatient intervention when managing fluid overload in patients hospitalized for acute systolic heart failure, and presenting with lower extremity edema. Also, compression stockings are mainstay devices in the outpatient setting for improving symptoms of lower extremity edema in chronic systolic heart failure. However, the utility of compression wraps in managing patients hospitalized for acute systolic heart failure, and transitioning to the use of compression stockings for symptom management upon discharge, has not been thoroughly assessed. Current practice suggests use of lower extremity compression wraps can facilitate intravenous diuresis while inpatient, achieve more optimal discharge dry weight, and lower BNP levels prior to discharge. Demonstrating efficacy of such a low-cost, low-risk intervention in decreasing hospital stay and achieving more favorable patient outcomes will have considerable impact on standard practice.

• SUBJECT POPULATION AND ELIGIBILITY

Inclusion criteria: patients age greater than 18 and less than 85 years of age, admitted to I5 with Acute Systolic Heart Failure, and an ejection fraction of less than 50% as determined by echocardiogram within 6 months, requiring inpatient management with intravenous diuretic therapy. Must have a diagnosis of acute systolic heart failure (by ICD coding) on admission, of any underlying etiology. Must have documentation of pitting edema on primary assessment.

Exclusion criteria: patients who do not meet inclusion criteria, who cannot tolerate IV diuresis, who cannot wear or tolerate lower extremity compression stockings or wraps; active diagnosis of ESRD on dialysis or peripheral neuropathy; ejection fraction greater than 50% as evaluated by echocardiogram within 6 months.

Control population: Patients meeting inclusion criteria, managed on I5 for acute systolic heart failure with standard medical therapy without the use of lower extremity compression wraps.

This will allow direct comparison of the effect of intervention (lower extremity compression wraps) on the previously listed endpoints on the same patient population.

Since this study evaluates an already established component of standard medical practice, there will be no discrimination of patient populations in enrollment outside of the inclusion and exclusion criteria.

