Patients will be enrolled exclusively based on inclusion and exclusion criteria, undergoing randomization into intervention or control groups. No screening tools will be used.

• STUDY PROCEDURES

The study will be an internally funded, parallel-intervention clinical trial studying the use of lower extremity compression stockings as adjuvant therapy to standard medical care in management of patients admitted for acute systolic heart failure. There will be two arms, intervention and control. 120 patients will be enrolled in the study, 60 to each arm, to achieve power above 80% with an alpha of 0.05, measuring continuous primary endpoints of average percent reduction in weight after diuresis, average change in BNP from admission to discharge, and average length of admission in days.

Data will be collected by Henry Ford personnel, for 120 patients previously admitted after January 2018 and managed on the HF Main cardiology I5 floor meeting inclusion criteria and managed with standard medical therapy without the use of compression stockings, and will undergo review by research team for enrollment into the control group. If additional patients are needed to achieve enrollment number of 60 control subjects, patients will be enrolled and randomized prospectively by the research team. Data collected retrospectively will be performed through Epic health medical record and charted on Excel spreadsheet, and will include admission length of stay, daily weights, daily urine outputs, daily diuretic dose and type(s) used, admission BNP, and discharge BNP. Research team will also perform chart review on enrolled patients to evaluate for 30-day readmission rate.

The intervention arm will include patients enrolled and randomized by the research team meeting inclusion criteria, and managed on HF Main cardiology I5 floor. This population will receive bilateral lower extremity compression wraps (ACE bandages) on day 1 of admission in addition to standard medical therapy. Data will be collected by the research team through Epic health medical record and will be charted on Excel spreadsheet, and will include admission length of stay, daily weights, daily urine outputs, daily diuretic dose and type(s) used, admission BNP, and discharge BNP. These charts will also undergo review by research team to evaluate for 30-day readmission rate.

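### Wrapped patients enter through consent and a day-1 wrap, but chart controls have no matching time zero or capacity screen, so length of stay may not be compared on like patients

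*Combined protocol and SAP*

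**What the plan says.** **Wrap arm.** Study Procedures states: "This population will receive bilateral lower extremity compression wraps (ACE bandages) on day 1 of admission in addition to standard medical therapy". The same section makes execution of the wrap order by the floor nurses the start of enrolment. Consent Process and Documentation requires consent before enrolment and bars patients with diminished capacity, a learning disability or any impairment.

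**Chart controls.** Study Procedures draws these from records: data are collected "for 120 patients previously admitted after January 2018 and managed on the HF Main cardiology I5 floor". That sentence goes on to require that they meet the inclusion criteria and were treated without compression. Prospective randomised controls are added only if the charts do not fill the 60 control places.

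**Criteria common to both.** Subject Population and Eligibility requires patients to be "admitted to I5 with Acute Systolic Heart Failure, and an ejection fraction of less than 50" percent, with the diagnosis present on admission, pitting edema at first assessment and a need for intravenous diuretics. It sets no time window and says nothing about capacity to consent.

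**Endpoint and analysis.** One of three primary endpoints is "Difference in length of admission in days". The start of that interval is not defined. The analysis is an unadjusted comparison of group means by t-test and ANOVA.

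**The concern.** When one group is entered at a fixed early moment and the other is picked from completed records, the two groups can differ in who was able to enter, apart from any treatment effect. Two routes are open here.

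- **Late arrival.** A patient treated elsewhere first and moved to I5 some days later may be impossible to wrap on day 1, yet that patient's chart may be accepted as a control. The days before I5 would then be counted in control only.
- **Capacity.** A patient too unwell to consent on day 1 cannot be enrolled and wrapped that day, but nothing in the chart-selection criteria removes a similar past patient from control.

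Length of stay is the endpoint most exposed, because days before I5 add to it directly. Extra days in control would favour wraps, which is the direction the trial hypothesises, and an unadjusted t-test would not correct for them. Percent change in BNP runs from admission to discharge and could also be affected, in an unknown direction. Weight change is defined around diuresis, not from admission, so its exposure is less direct.

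**Working it through.** **1. Where the two groups differ**

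| Entry element | Wrap arm | Chart controls |
|---|---|---|
| Inclusion criteria, including admission to I5 | Yes | Yes |
| Managed on I5 | Yes | Yes |
| Treatment anchor on day 1 | Yes | None |
| Event that starts enrolment | Wrap order executed | None |
| Consent and capacity screen | Yes | Not among the chart criteria |

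The ward wording is the same for both groups. The differences lie in the last three rows.

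**2. What follows under each reading of the undefined terms**

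| Day 1 counts from | I5 admission criterion covers transfers? | Late arrivals in wrap arm | Late arrivals in control |
|---|---|---|---|
| Hospital admission | Yes | Not as specified | Possible |
| Hospital admission | No | No | No |
| I5 arrival | Yes | Possible | Possible |
| I5 arrival | No | No | No |

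The late-arrival route is one-sided only in the first row. In the third row both groups may contain such patients, but the start of length of stay is still unstated. The capacity route is open in all four rows.

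**3. The plan's own figure**

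The plan gives: "120 patients will be enrolled in the study, 60 to each arm, to achieve power above 80% with an alpha of 0.05". It states no difference or SD for length of stay, so this cannot be reproduced. What can be solved is the detectable difference, using a two-sided test and the normal approximation (the plan does not state sidedness):

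d = (1.960 + 0.842) × √(2/60) = 2.802 × 0.1826 = 0.511 SD

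With an assumed SD of 4 days this is 0.511 × 4 = 2.05 days.

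**4. Size of a possible shift in length of stay**

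Every input here is an assumption except 60 per arm and alpha 0.05. Let f be the share of controls with time before I5, and k the extra days each.

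Shift in control mean = f × k

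- Low: 0.05 × 2 = 0.1 days
- Middle: 0.15 × 3 = 0.45 days
- High: 0.25 × 4 = 1.0 days

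Standard error of the difference at SD 4 = 4 × √(2/60) = 0.730 days. Noncentrality = shift / 0.730. The rejection probability with no wrap effect is from the noncentral t, 118 df, two-sided 0.05 (critical value 1.980).

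| Shift (days) | Noncentrality | False-positive rate, SD 4 |
|---|---|---|
| 0.1 | 0.137 | 0.052 |
| 0.45 | 0.616 | 0.094 |
| 1.0 | 1.369 | 0.274 |

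For the 0.45-day shift the rate is 0.129 at SD 3 and 0.078 at SD 5. The table holds the SD at 4 in both groups. A separate normal-approximation check allowed for the extra variance in control: 20% of controls with 2 extra days (0.4 days) gave 0.084 at SD 4.

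The middle shift is 0.45/2.05 = 22% of the detectable difference, and the high one is 1.0/2.05 = 49%.

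**The case against.** A reader might infer that chart controls need only have spent some time on I5. The text does not support that. They must also meet the inclusion criteria, which include admission to I5 and a diagnosis on admission. A plain reading of the first could exclude someone who was admitted to another unit and moved later. Nor is being managed on I5 a looser test for controls, since the wrap arm is described the same way.

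It is also tempting to say that late arrivals are barred from wraps. Day 1 is written as a treatment procedure, not as an eligibility criterion, and Study Procedures says enrolment rests on the inclusion and exclusion criteria alone. Consent on day 1 is a fair inference from the sequence of consent, order and wrap. It is not a stated rule.

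The direction is open to challenge too. Patients discharged before anyone could approach them may appear as chart controls but not in the wrap arm, and that would shorten control stay. The magnitude rests on no figure from the plan; its low end is close to nominal, and the 27% is the extreme corner of the assumed range.

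All of these points stand, and they rule out a claim of demonstrated bias in favour of wraps. They do not supply chart controls with a time zero, say where length of admission begins, or explain why the capacity exclusion is absent from the chart criteria.

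**Conclusion.** The concern holds in a limited form. The wrap arm has a working entry point on day 1; chart controls have none, and they do not pass the capacity screen. Because the start of admission and the status of transfers are undefined, patients who arrived late on I5 or could not have consented on day 1 may enter control only.

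Extra pre-I5 days would by themselves lengthen control stay, but a reader should not conclude that the comparison is bound to favour wraps. The late-arrival route needs one particular pair of readings, and early discharges could pull the other way. Under the assumed shifts of 0.1 to 1.0 days, with SD 4 and 60 per arm, the false-positive rate on length of stay runs from about 5% to about 27%, that is, from negligible to material. The documents do not narrow that range. For BNP and weight the direction is unknown.

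This should be changed, because the remedy affects who enters control and costs little.

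**What to change.** 1. Define one time zero, stating whether it is hospital admission or arrival on I5. Use it for day 1 and for the start of length of stay in both groups.
2. State whether the I5 admission criterion includes patients transferred from other units.
3. Apply one entry condition to chart and prospective patients: on I5, with intravenous diuretic started, by day 1 counted from that time zero. Check it in charts from the bed-location and medication records. The diuretic timing is an addition to the current criteria, which require only that such therapy is needed.
4. Apply the capacity and impairment exclusion from the consent section to charts, where the record documents it.

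**Cost.** Protocol wording and two more chart fields (I5 arrival date and first intravenous diuretic date). Fewer charts will qualify, but 120 are planned for review against 60 control places, so there is some room. Prospective patients identified after day 1 would not be enrolled. Capacity is likely to be recorded incompletely in past charts, so that step will be partial. None of this removes the other biases of non-randomised historical controls.

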Co-investigators will be responsible for retrospective and prospective data review for control population. Both co-investigators and sub-investigators will be responsible for enrolling patients in the study and collecting above mentioned data points. Nursing staff on the floor will undergo teaching on application of ACE compression wraps, and will be responsible for capturing physician order for wrap application and executing order, which will mark the beginning of the trial enrollment.

Data analysis will be conducted through the Division of Biostatistics and Research Epidemiology and will include descriptive statistics and univariate comparisons between treatment groups. T-test and ANOVA with post-hoc analysis will be used to evaluate for difference in the means of each endpoint previously listed for each treatment group. Patient information will be de-

identified prior to data analysis. Data for enrolled patients will be saved on secure Henry Ford Health System servers on Microsoft OneDrive cloud servers and shared among research team. Identifiers will include MRNs to access patient charts, collect and verify data, and perform review for 30-day readmission rates. Data will be stored for the entirety of the study, and promptly discarded in accordance with HFHS regulation at the completion of the study tentatively scheduled for January 2021. Data collected on patients excluded from the study will be discarded at the time of exclusion in accordance with HFHS regulation. Missing or incomplete data will prompt withdrawal of particular patient from study, and will factor into final data analysis as an intention to treat value.

Total time of subject enrollment in the study: duration of hospital stay. No additional visits or follow-up testing is required.

Literacy and language barrier concerns will be handled on a case-by-case basis, primarily using standard communication methods of translator services.

- **ANTICIPATED RISKS**

There are no significant anticipated risk beyond standard of care risk in management of patients with acute systolic heart failure. Intervention includes an already established therapy on patients with lower extremity edema. We are simply testing the formal efficacy of this intervention in an interventional study.

- **ANTICIPATED BENEFITS**

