Anticipated benefits include: decreased length of stay, decreased amount of diuretic used, increased percentage of weight achieved through diuresis; greater percent of BNP reduction; decreased 30-day readmission rate.

- **RENUMERATION/COMPENSATION**

No compensation offered

- **COSTS**

There is no additional cost anticipated for this study outside of standard medical management of acute systolic heart failure and any additional medical conditions treated during the hospital admission.

- **ALTERNATIVES**

Intervention does not involve offering an established efficacious therapy to patients, and conversely control group is not being withheld from any known therapy that affects morbidity/mortality. No known alternatives.

- **CONSENT PROCESS AND DOCUMENTATION**

Co-investigators and sub-investigators enrolling patients will be responsible for obtaining consent from patients prior to enrollment. This will involve presentation of consent document with description of study. Patients will have the opportunity to privately ask questions and receive answers at the time of enrollment after the study is described to them in detail, including risks and benefits. There will be no duress or undue influence, as intervention is already a standard of medical practice. Patients will have the opportunity to refuse intervention. Patients will not be enrolled if they have diminished capacity or learning disability, or impairment of any kind. If patient is non-English speaking, consent form will be translated using standard translator services (in person translator, translator phone). Consent documentation will be stored on the Henry Ford secured OneDrive Microsoft cloud server. This information will only be accessible by research team. Information will be stored for the entirety of the study, and promptly discarded in accordance with HFHS regulation at the completion of the study tentatively scheduled for January 2020. Information collected on patients excluded from the study will be discarded at the time of exclusion in accordance with HFHS regulation.

- **WITHDRAWAL OF SUBJECTS**

Patients withdrawn from study will be notified, and information gathered from enrollment period will be analyzed as intention to treat. All information will be destroyed appropriately at the time of withdrawal.

- **PRIVACY AND CONFIDENTIALITY**

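### Enrolment is said to start when the wrap order is executed, which cannot happen in a control and conflicts with enrolment at consent and randomisation; if followed, never-wrapped patients could be lost from the intervention arm only.

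*Combined protocol and SAP*

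**What the plan says.** All references are to the combined protocol and SAP.

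- **Start of enrolment (Study Procedures).** Nursing staff are responsible for "capturing physician order for wrap application and executing order, which will mark the beginning of the trial enrollment". No other event is named as the start.
- **Who is wrapped (Study Procedures).** Of the intervention arm: "This population will receive bilateral lower extremity compression wraps (ACE bandages) on day 1 of admission in addition to standard medical therapy". Controls are patients "managed on I5 for acute systolic heart failure with standard medical therapy without the use of lower extremity compression wraps" (Subject Population and Eligibility).
- **How patients enter, stated differently.** Subject Population and Eligibility says: "Patients will be enrolled exclusively based on inclusion and exclusion criteria, undergoing randomization into intervention or control groups". Study Procedures says: "The intervention arm will include patients enrolled and randomized by the research team meeting inclusion criteria". The consent section has investigators obtain consent before enrolment, and adds: "Patients will have the opportunity to refuse intervention".
- **How controls enter (Study Procedures).** Charts of 120 earlier admissions "will undergo review by research team for enrollment into the control group". Randomised controls are a reserve: "If additional patients are needed to achieve enrollment number of 60 control subjects, patients will be enrolled and randomized prospectively by the research team".
- **Intention to treat.** The phrase appears twice: in Study Procedures for patients withdrawn because of missing or incomplete data, and in Withdrawal of Subjects for information from the enrolment period of withdrawn patients. The latter section also has withdrawn patients' information destroyed at withdrawal. Study Procedures has excluded patients' data discarded at exclusion.

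**The concern.** A comparison by allocation needs entry to the analysis fixed by an event that both arms share and that precedes treatment. Executing a wrap order is neither: it follows allocation, and only one arm can have it.

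A patient allocated to wraps whose order is never carried out has been randomised according to the eligibility section, but has not begun enrolment according to the nursing sentence. If the team works from the nursing sentence, that patient leaves the intervention arm, and a similar patient allocated to control faces no such test. The wrapped group is then chosen partly by what happened after allocation.

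All three primary endpoints (percentage weight change, percentage BNP change, length of stay) would be exposed. The planned analysis is descriptive statistics, univariate comparisons, t-tests and ANOVA, none of which corrects for such selection.

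**Working it through.** **Step 1. Setting the statements side by side.**

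| Question | Nursing sentence, Study Procedures | Eligibility, arm definition and consent text |
|---|---|---|
| What starts enrolment? | Execution of the wrap order | Eligibility, consent and randomisation |
| Can it occur in a control? | No | Yes, for a prospective control |
| Is a patient allocated to wraps but not wrapped in the trial? | No | Yes |

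The two columns give different analysis sets for the intervention arm, and nothing says which governs.

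**Step 2. Does the intention-to-treat wording settle it?** It covers withdrawal for missing data and other withdrawals, and in the second case only information from the enrolment period. Under the nursing sentence that period never begins for a never-wrapped patient. If such a patient is handled as withdrawn or excluded, the text calls for the information to be destroyed or discarded. No sentence clearly keeps the patient in the intervention arm.

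**Step 3. The plan's own figure.** The plan gives 60 per arm, power above 80% and alpha 0.05, but no effect size, SD or sidedness, so the sample size cannot be reproduced. Solving backwards with the two-sample t-test at two-sided 5%, 60 per arm gives 80% power at a difference of 0.516 SD. This serves only as a yardstick.

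**Step 4. Size under assumed values.** The documents give no never-wrapped rate and no prognostic difference. Assume:

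- q = share of allocated wrap patients never wrapped, 5% to 15%
- g = difference in mean outcome between wrapped and never-wrapped patients, 0.5 to 1 SD, in either direction
- no true treatment effect
- a control arm of 60 that matches the allocated wrap arm, as randomised controls would

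The allocated-arm mean is (1 − q) × wrapped mean + q × never-wrapped mean. Hence wrapped mean − allocated mean = q × g, which is the bias.

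With n₁ = 60(1 − q) and n₂ = 60, SE = √(1/n₁ + 1/n₂) in SD units. The noncentrality is q × g / SE, and the rejection probability comes from the noncentral t with n₁ + n₂ − 2 degrees of freedom.

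| q | g (SD) | n₁ | Bias (SD) | SE (SD) | Noncentrality | Bias / 0.516 | Two-sided rejection rate |
|---|---|---|---|---|---|---|---|
| 5% | 0.5 | 57 | 0.025 | 0.185 | 0.135 | 5% | 5.2% |
| 5% | 1.0 | 57 | 0.050 | 0.185 | 0.270 | 10% | 5.8% |
| 10% | 0.5 | 54 | 0.050 | 0.188 | 0.267 | 10% | 5.8% |
| 10% | 1.0 | 54 | 0.100 | 0.188 | 0.533 | 19% | 8.3% |
| 15% | 0.5 | 51 | 0.075 | 0.190 | 0.394 | 15% | 6.8% |
| 15% | 1.0 | 51 | 0.150 | 0.190 | 0.788 | 29% | 12.2% |

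The sign of g decides which arm is favoured; the two-sided rejection rate is the same either way. If recruitment ran on until 60 patients had been wrapped, the bias would be unchanged and the rate similar: 0.15 SD gives 13.0% with 60 per arm and a normal approximation.

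**Step 5. Which controls this applies to.** The calculation isolates the effect of the rule against controls who were themselves randomised. Chart-review controls were never allocated, so selection in the wrap arm adds to whatever difference already exists, and the two cannot be separated.

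**The case against.** The best case for the plan is that the nursing sentence is only an operational marker. The sentence just before it makes investigators responsible for enrolling patients, and the eligibility section bases enrolment on the criteria alone. On that reading every randomised patient is kept. This is a fair reading, and it limits the point: a reader might infer that the plan removes never-wrapped patients, but no sentence says so. The loss follows only if the nursing sentence governs. What stands is that the sentence is the only stated start of enrolment, and the text does not subordinate it to the others.

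Four further objections are sound in part.

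- **Outcome windows.** Weight is compared before and after diuresis, BNP from admission to discharge, and stay over the whole admission. None is clocked from enrolment, so a different start does not shift them. Only selection of patients can cause bias.
- **Opportunity.** Wraps go on during day 1, and patients who cannot wear or tolerate them are excluded beforehand. The right to refuse stands in the consent section and may mean declining before entry. The never-wrapped share may therefore be small, and at the low end of the range the effect is negligible.
- **Direction.** A reader might infer that the lost patients do worse, so that wraps are flattered. The documents do not support this. A patient discharged before wrapping has a short stay, and losing that patient counts against wraps on that endpoint. Refusers need not have a poor prognosis.
- **Controls.** A reader might infer that a selected wrap arm is set against unselected controls within a randomised comparison. Controls come mainly from charts chosen for management without compression, and randomised controls are added only if charts supply fewer than 60. There may be none.

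Nor is it right that the plan contradicts a general intention-to-treat commitment. It makes none; the phrase is tied to missing data and withdrawals.

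**Conclusion.** The point holds as an unresolved conflict over when enrolment begins, one reading of which conditions the intervention arm alone on an event after allocation. It should be corrected, but it is secondary to the non-randomised source of most controls.

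Its size and direction cannot be found from the documents. For 5-15% never wrapped and a difference of 0.5-1 SD, the bias is 0.025-0.15 SD in either direction, or 5-29% of the difference detectable at 80% power, with a false-positive rate of 5.2-12.2%. These figures rest wholly on the assumed rate and difference, and describe the comparison with randomised controls only.

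**What to change.** 1. Replace the nursing clause with a rule that enrolment of every prospective patient, in either arm, is the moment of randomisation after consent, whether or not a wrap order is executed.
2. State that every randomised patient is analysed in the allocated arm.
3. Record whether and when wraps were applied as a treatment-delivery variable only.
4. Index any chart control that is kept at the matching admission time point, since such a patient has no randomisation time.
5. Reconcile the text on discarding excluded patients' data (Study Procedures) and destroying withdrawn patients' information (Withdrawal of Subjects), so that never-wrapped patients' data are kept as far as consent allows.

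The cost is rewording in three sections (eligibility, procedures, withdrawal) and a check that the consent form permits retention; no new type of data is needed. Never-wrapped patients will dilute the estimated effect a little, which is the usual price of analysis by allocation. The change does not make the comparison with chart controls a randomised one.

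### BNP percent change is compared between arms without using admission BNP; two pre-specified log-scale analyses, with and without that covariate, would usually be more efficient

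*Combined protocol and SAP*

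**What the plan says.** The design abstract lists as the second of three primary endpoints "Percent difference in Brain natriuretic peptide (BNP) from admission to discharge", and the hypothesis there is that wrapping "increases percent reduction in BNP after diuresis". Anticipated Benefits also speaks of BNP in percent terms.

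The power sentence in Study Procedures claims power above 80% at alpha 0.05 with 60 patients per arm. It describes the endpoints as "average percent reduction in weight after diuresis, average change in BNP from admission to discharge" and length of stay, so it keeps percent for weight but not for BNP.

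The analysis paragraph of the same section plans "descriptive statistics and univariate comparisons between treatment groups" and then: "T-test and ANOVA with post-hoc analysis will be used to evaluate for difference in the means of each endpoint". Nowhere is baseline adjustment, a log transformation or a sensitivity analysis for BNP mentioned.

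The data lists for both arms include "daily urine outputs, daily diuretic dose and type(s) used, admission BNP, and discharge BNP". Control data are taken first "for 120 patients previously admitted after January 2018". Prospective randomised controls are added only as a top-up: "If additional patients are needed to achieve enrollment number of 60 control subjects".

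**The concern.** With two arms, ANOVA is the same test as the t-test and does not bring in a covariate. The plan therefore compares mean percent change and leaves the admission-discharge relation unused. If BNP is right-skewed (an assumption; the documents give no distribution), percent change is an awkward scale for a t-test: it cannot fall below -100% but has no upper limit, so a few large rises can dominate the SD.

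Two things are at stake. One is power for a primary endpoint at a fixed 60 per arm. The other is interpretation: controls come mainly from past admissions, so admission BNP may differ between arms, and the plan has no analysis that would show how far the BNP result depends on that difference.

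**Working it through.** **The plan's own figure.** Power above 80% can be neither reproduced nor refuted, because no effect size or SD is given. At 60 per arm and two-sided alpha 0.05 (sidedness is not stated), 80% power needs a standardised difference of (1.960 + 0.842) x sqrt(2/60) = 0.511.

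**Inputs.** From the documents: 60 per arm and alpha 0.05. Assumed: lognormal BNP, median fall of 35% in controls, discharge BNP 30% lower with wraps (ratio 0.70), log-SD 0.6-1.0 and equal at both times, admission-discharge correlation rho 0.5-0.8 on the log scale.

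**Power.** Percent in 10,000 simulated trials per cell, for percent change / unadjusted log-ratio / log ANCOVA:

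| log-SD | rho 0.5 | rho 0.6 | rho 0.7 | rho 0.8 |
|---|---|---|---|---|
| 0.6 | 84/90/96 | 91/95/98 | 98/99/99 | 100/100/100 |
| 0.8 | 55/67/80 | 67/77/86 | 82/88/92 | 95/97/98 |
| 1.0 | 34/50/61 | 44/58/68 | 58/71/77 | 79/86/90 |

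Repeat runs agree to about 1 point; the lowest cell also came out at 34/49/60.

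**Check by formula** (log-SD 0.8, rho 0.6; effect ln 0.70 = -0.357):

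- Log-ratio: SD = 0.8 x sqrt(2 x 0.4) = 0.716; SE = 0.716 x sqrt(2/60) = 0.131; 0.357/0.131 = 2.73; power = Phi(2.73 - 1.96) = 78% (simulated 77%).
- ANCOVA: SD = 0.8 x sqrt(1 - 0.36) = 0.640; SE = 0.117; 0.357/0.117 = 3.05; power = Phi(1.09) = 86% (simulated 86%).

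**Crossing 80%.** Percent change is below 80% in 6 of 12 cells. ANCOVA is below it in 3 or 4, since the cell printed as 80 falls on either side by simulation noise. Moving from percent change to ANCOVA therefore decides the 80% claim in 6 - 4 = 2 or 6 - 3 = 3 cells. Outside the cells where percent change already exceeds 90%, the gain is about 10 to 27 points (82 to 92; 34 to 61).

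**Sensitivity of the gain.**

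- The variance of ANCOVA relative to the log-ratio is k^2(1 - rho^2)/(1 + k^2 - 2 rho k), where k is discharge log-SD over admission log-SD. At k = 1 this is (1 + rho)/2, or 0.75 at rho 0.5 and 0.90 at rho 0.8.
- At k = 1.2 and rho 0.7 it is 1.44 x 0.51 / (2.44 - 1.68) = 0.966; at rho 0.8 it is 0.997. The covariate then adds only about 0-5 points over the log scale alone.
- At rho 0.9 (k = 1) the gain of ANCOVA over percent change is 0-1 point.
- If percent change is in fact symmetric and unrelated to admission BNP, log ANCOVA loses 0-5 points.

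**False positives.** With comparable arms, percent change gives 4.2-5.3% and ANCOVA 4.7-5.5%. With no effect and a 0.4 SD difference in log admission BNP:

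| If the truth is | percent change | log-ratio | ANCOVA |
|---|---|---|---|
| discharge depends on admission alike in both groups | 9-17% | 10-20% | about 5% |
| the same shift is present at both times | 4-5% | 5% | 11-23% |

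The two log-scale estimates differ by exactly (1 - fitted slope) x the difference in mean log admission BNP. At 0.4 SD that is about (1 - 0.8) x 0.4 x 0.6 = 0.048 to (1 - 0.5) x 0.4 x 1.0 = 0.20 log units, so the ratios lie 5-22% apart.

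**Effect of requiring agreement.** The chance that both tests reject cannot exceed the smaller of the two. Under either row above, false positives are then held to about 5% or less. Power is likewise capped at about that of the log-ratio. From the power grid, the gain over percent change becomes 0 to 16 points (34 to 50 at most), and only one cell moves across 80% (79 to 86).

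**The case against.** The strongest reply is that nothing here is wrong. A comparison of mean percent change matches the stated endpoint and hypothesis and holds its 5% level when the arms are comparable. That stands, and it is why this is put as an improvement.

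It also stands that every input to the power comparison is assumed, that the gain may be anywhere from nothing to substantial, and that part of it comes from the log scale and not from the covariate. The move to a ratio of geometric means changes the summary measure of a primary endpoint. The analysis paragraph says what the analysis will include, which does not strictly exclude adjustment; still, none is named.

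A reader might go further in three ways that the documents do not support:

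- *That the planned t-test is invalid, or that BNP is underpowered.* With no SD, effect or correlation given, neither can be shown; in half of the assumed settings percent change has more than 80% power.
- *That ANCOVA should simply replace the t-test.* Controls are filled first from past admissions. If those patients differ by a stable amount at both times, ANCOVA has 11-23% false positives where percent change has 4-5%. The documents cannot show which model holds.
- *That the power sentence defines an absolute BNP change.* It only leaves the scale unstated; the endpoint list, hypothesis and anticipated benefits all use percent. This is a wording gap to close and adds no weight to the analysis point.

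**Conclusion.** The point holds as a cheap efficiency improvement to a valid analysis. Its size rests on assumed lognormal BNP, a 30% effect, log-SD 0.6-1.0, rho 0.5-0.8 and equal log-SD at both times. Within that range, using the log scale and admission BNP can add up to about 27 points of power, but often adds little. With the safeguard that the historical controls call for, the usable gain is nearer that of the log-ratio test. The benefit to interpretation does not need a power gain: showing both estimates beside the admission difference tells the reader how far the BNP result depends on what is assumed about the controls. It does not remove confounding from a non-randomised control group, which remains the larger problem.

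**What to change.** - Define BNP on one relative (percent or ratio) scale in the endpoint list, the power sentence and the analysis paragraph.
- Pre-specify two log-scale analyses of equal prominence, each reported as a ratio of geometric means with 95% CI: (a) ANCOVA of log discharge BNP on arm and log admission BNP; (b) the unadjusted comparison of log(discharge/admission). A ratio of 0.70 in (a) reads as 30% lower discharge BNP at equal admission BNP.
- Show the between-arm difference in admission BNP beside them, and keep mean percent change by arm as a descriptive summary.
- While historical controls are used, claim a BNP benefit only if both analyses support it. Otherwise report the result as depending on the assumption about those controls.

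No change is proposed for weight or length of stay.

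Cost: SAP wording and a few lines of code; no new data. Downsides: the result is a ratio in place of a mean percent; the gain is small at high correlation; up to about 5 points of power may be lost if percent change is symmetric and unrelated to admission BNP; and requiring agreement limits power to about that of the log-ratio test.
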